1.0 RESEARCH HYPOTHESIS

Anti-PD1 antibody (nivolumab) alone or in combination with anti-CTLA-4 antibody (ipilimumab) can be safely administered and may induce augmented immunological and clinical responses in patients with resectable hepatocellular carcinoma (HCC).

2.0 OBJECTIVES

Primary Objective:

1. To evaluate the safety and tolerability of therapy with nivolumab alone or nivolumab + ipilimumab in resectable HCC in the context of presurgical therapy.

Note: As of January 8, 2020, 30 patients have been enrolled and 27 patients have been randomized. The PI decided to stop enrollment since the study has reached its primary endpoint of safety.

Secondary Objectives:

1. To assess the efficacy of presurgical nivolumab alone or nivolumab + ipilimumab therapy in HCC by estimating the objective response rate (ORR) and time to progression (TTP) per RECIST 1.1 progression-free survival (PFS).

Exploratory Objectives:

1. To assess the *immunological/biomarker changes* in tumor tissues and peripheral blood in response to nivolumab alone or nivolumab + ipilimumab in HCC therapy (pre- vs post-treatment), and explore any potential association between these biomarker measures and antitumor response and immune-related response criteria (iRC) assessed by MD Anderson Department of Diagnostic Imaging.

[figure not shown]

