Patients in **Arm A (resectable cohort)** will receive nivolumab at 240 mg IV every 2 weeks for 3 doses followed by liver imaging and hepatic resection on day 1 of week 7, followed (after 4 weeks from surgery) by nivolumab 480 mg IV every 4 weeks in the adjuvant setting until disease progression or for 2 years, whichever is sooner. Patients in **Arm B (resectable cohort)** will receive nivolumab 240 mg IV every 2 weeks for 3 doses plus ipilimumab 1 mg/kg IV on day 1 of therapy (3 doses of nivolumab, 1 dose of ipilimumab) followed by hepatic resection followed (after 4 weeks from surgery) by nivolumab 480 mg IV every 4 weeks plus ipilimumab 1 mg/kg IV every 6 weeks to 4 doses in the adjuvant setting. Adjuvant therapy will start after 4 weeks from surgery with nivolumab 480 mg IV every 4 weeks (Both Arms A and B) plus ipilimumab 1 mg/kg IV every 6 weeks (in Arm B only) for up to 4 doses in the adjuvant setting until disease recurrence or for total of 2 years from first cycle, whichever is sooner. For Arm B, ipilimumab will be administered before nivolumab since the toxicities for ipilimumab are already well-known. Since the doses of nivolumab and ipilimumab either as monotherapy or combination are within maximum tolerated doses as previously defined, no dose increases or reductions will be allowed.

Patients will return at week 6 for a pre-surgical evaluation. A small portion of patients with rapid disease progression (We anticipate 1-3 of a total of 30 patients in Arms A and B) may not have hepatic resection per discretion of the treating surgical and medical oncologists. These patients will be off protocol and treated with other standard or investigational agents. They will be asked to return for an optional biopsy that will be scheduled in place of their surgery. For patients who had significant progression of disease pre-operatively but are still eligible for hepatic resection or transplantation, they will be treated with other investigational agents vs. observation post-operatively as there is no standard adjuvant therapy in surgically resected HCC.

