12.0 STATISTICAL METHODOLOGY

12.1 Preliminaries and Objectives

This is a randomized, pilot trial of nivolumab (Arm A) or nivolumab + ipilimumab (Arm B) as pre-operative treatment for patients with hepatocellular carcinoma who are eligible for surgical resection. Each patient in both Arms A and B will be given nivolumab at 240 mg every 2 weeks

for a total of 6 weeks. Patients in Arm B will additionally be treated concurrently with ipilimumab at 1mg/kg every 6 weeks. No dose increases or reductions will be allowed for nivolumab or ipilimumab. Surgical resection or post-treatment biopsy will occur within 4 weeks after finishing the last cycle of therapy. The rationale is that nivolumab and ipilimumab activate the immune system via distinct mechanisms and therefore, the combination of nivolumab and ipilimumab may result in synergistic activation of the immune system against hepatocellular carcinoma. The primary objective is to assess the safety and tolerability of nivolumab +/- ipilimumab. Secondary objectives include estimating the ORR and TTP of the 2 different arms. Exploratory objectives include evaluating the pre- and post-treatment immunological changes in tumor tissues and peripheral blood.

As of January 8, 2020, 30 patients have been enrolled and 27 patients have been randomized. The PI decided to stop enrollment since the study has reached its primary endpoint of safety.

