12.2.2 Secondary Endpoints

12.2.2.1. *Objective Response Rate (ORR)*

Objective response rate (ORR) is defined as the number of subjects with a best response of CR or PR after 12 weeks of therapy by RECIST 1.1 criteria divided by the number of randomized subjects as described in Section 10.3.4.2

12.2.2.2. *Time to progression (TTP)*

TTP is defined as the time from the start of study drug to the first documented tumor progression or recurrence of tumor as determined by the investigator using RECIST 1.1 or iRC criteria. Patients who are alive and free of known progression at the time of analysis will be censored on the date of last tumor assessment.

12.2.2.3 *PFS*

PFS is defined as the time from the start of treatment to date of PD or recurrence or date of death whichever occurs first if patients have a event, or to the last follow-up date if patients are alive without PD.

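### TTP and PFS are named as measures of presurgical efficacy, but they run through resection and adjuvant treatment and so describe the whole perioperative strategy

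*Combined protocol and SAP*

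**What the plan says.** **Objective.** Section 2.0 gives the secondary objective as "To assess the efficacy of presurgical nivolumab alone or nivolumab + ipilimumab therapy in HCC". The measures it names are ORR, TTP and PFS. Section 10.3.4.1 lists PFS and ORR among the main efficacy assessments.

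**How the statistical section describes the arms.** Section 12.1 opens: "This is a randomized, pilot trial of nivolumab (Arm A) or nivolumab + ipilimumab (Arm B) as pre-operative treatment". It sets out 6 weeks of nivolumab in both arms, with ipilimumab added in Arm B, followed by surgery. It does not mention adjuvant treatment.

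**What patients are planned to receive.** Under 5.3, both arms have three presurgical nivolumab doses, and Arm B has one ipilimumab dose on day 1. Resection is on day 1 of week 7. Both arms start nivolumab 480 mg every 4 weeks once four weeks have passed since surgery. The adjuvant difference between the arms is worded this way: "plus ipilimumab 1 mg/kg IV every 6 weeks (in Arm B only) for up to 4 doses in the adjuvant setting until disease recurrence". The same sentence limits the adjuvant phase to two years, counted from cycle 1. Footnote r of the Arm B schedule repeats the cap of four ipilimumab doses.

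**Endpoint clocks.** "PFS is defined as the time from the start of treatment to date of PD or recurrence or date of death" (12.2.2.3). TTP also starts at first study drug and ends at progression or recurrence (12.2.2.2). Neither has a landmark or censoring rule at surgery or at the start of adjuvant treatment.

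**Planned use.** Section 12.6 plans Kaplan-Meier PFS by arm. It also says that TTP with confidence intervals, together with the response profile and the 6-month clinical benefit rate, will guide future development. The only between-arm efficacy test is Fisher's exact test on response rates.

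**The concern.** The objective names one treatment component and the endpoints measure another quantity. A TTP or PFS curve from this trial reflects presurgical drug, resection and adjuvant drug together, and nothing in 12.2.2 or 12.6 separates them. This affects both uses of the curves:

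- **Within an arm**, the estimate includes resection and a long adjuvant nivolumab course.
- **Between arms**, a descriptive difference includes the adjuvant ipilimumab given only in Arm B.

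If the objective is followed as written, either quantity would be reported as efficacy of three presurgical nivolumab doses with or without one ipilimumab dose. Because 12.1 defines the arms only by their pre-operative treatment, a reader of the statistical section alone would have no warning. The stake is the label on an estimate that 12.6 intends to use when planning later work.

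**Working it through.** **The plan's own figure.** No rate, hazard ratio, event count or power is stated for TTP or PFS. The only power-type figure concerns response (12.6): more than 90% probability of at least one response in 15 patients if the true rate is 15%. Check: 1 − 0.85^15 = 0.913. It reproduces, and it has no bearing on TTP or PFS.

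**Timeline from 5.3.** Count weeks from first dose. Surgery falls at week 6 (day 1 of week 7), adjuvant treatment starts at week 10, and the limit of 2 years from first cycle is week 104.

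- Presurgical share of the planned period: 6/104 = 5.8%.
- Arm B ipilimumab: 1 presurgical dose and up to 4 adjuvant doses, so up to 4/5 = 80% is adjuvant. The adjuvant doses fall at about weeks 10, 16, 22 and 28. That is 18 weeks from first to last, or 24 weeks (weeks 10 to 34) if each dose covers 6 weeks.
- Nivolumab, planned identically in both arms: 3 × 240 = 720 mg presurgical. Adjuvant dosing every 4 weeks from week 10 to week 102 is 24 × 480 = 11,520 mg. The presurgical share is 720/12,240 = 5.9%. This share bears on each arm's own estimate, not on the difference between arms.

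**Where the events would fall.** Assume a constant hazard λ. Section 3.2 reports 5-year recurrence after resection as high as 70%, so λ = −ln(0.30)/5 = 0.2408 per year. Applying it from first dose is a simplification.

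- By week 6: 1 − exp(−0.2408 × 42/365.25) = 2.7%.
- By week 10: 1 − exp(−0.2408 × 70/365.25) = 4.5%.
- By 2 years: 1 − exp(−0.4816) = 38.2%.
- Share of 2-year events after adjuvant start: 1 − 4.5/38.2 = 88%.

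**How large a difference could arise with no presurgical effect.** Let presurgical ipilimumab do nothing, and let adjuvant ipilimumab multiply the hazard by HR from t0 = 70 days = 0.192 years. The HR values are assumptions; the documents give none.

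- Arm A at 2 years: exp(−2λ) = 61.8%.
- Arm B, effect for 24 weeks (0.460 years): 61.8% × exp[λ(1 − HR) × 0.460].
- Arm B, effect sustained to 2 years: exp[−λ(0.192 + HR × 1.808)].

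| Assumed HR | Gain, 24-week effect | Gain, sustained effect |
|---|---|---|
| 0.8 | 1.4 points | 5.6 points |
| 0.7 | 2.1 points | 8.6 points |
| 0.5 | 3.5 points | 15.0 points |

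Section 3.4.5 gives recurrence of about 50% or more without a time horizon. Read as a 5-year figure, it gives gains of 1.0, 1.5 and 2.5 points (24 weeks) or 3.9, 5.9 and 10.1 points (sustained).

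**Does ORR fill the gap?** Not as defined. Section 12.2.2.1 takes best response after 12 weeks of therapy, and the summary-report paragraph in 12.6 assesses response at week 14. Planned resection is on day 1 of week 7, before both. Section 5.3 does schedule a scan at week 6, before surgery, but no secondary endpoint is tied to it.

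**The case against.** The case for leaving the plan alone has several sound parts.

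- **Descriptive pilot.** No TTP or PFS comparison is planned. Section 12.3 calls the secondary results preliminary estimates, and 12.1 words the objective neutrally, as estimating ORR and TTP of the two arms. Section 3.2 speaks of PFS data with the combination, without limiting it to the presurgical phase. All of this stands, so there is no invalid hypothesis test here.
- **Small arm difference.** A reader might infer that the arms differ by two years of adjuvant drug. They do not: the two-year drug is nivolumab, planned identically in both. The planned adjuvant difference is at most four ipilimumab doses.
- **Noise.** With 15 per arm and complete follow-up, the standard error of a 2-year difference in the most extreme row is √(0.618 × 0.382/15 + 0.768 × 0.232/15) = 16.6 points, larger than the 15.0-point gain itself. The trial could not reliably show such a difference. That limits the between-arm worry, but it does not make either arm's own estimate a measure of presurgical effect.
- **Decision rule.** A reader might infer that a presurgical-only trial would be launched on a misread TTP. The documents plan no such trial, and the launch signal in 12.6 is at least one response per arm. TTP is one of three descriptive inputs.

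What remains is that 2.0 assigns TTP and PFS to a question they cannot answer, 12.1 leaves out the phase that explains why, and 12.6 gives TTP a stated use.

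**Conclusion.** The point holds as an attribution error. TTP and PFS as defined estimate the outcome of presurgical drug, resection and adjuvant drug combined, and cannot support the statement about presurgical efficacy in 2.0. This follows from the text and needs no numerical assumption.

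The size does rest on assumptions: constant hazard, recurrence figures from the background sections applied from first dose, and invented hazard ratios. On those, adjuvant ipilimumab alone could move Arm B's 2-year progression-free probability by between 1.0 points (50% recurrence, HR 0.8, 24 weeks) and 15.0 points (70% recurrence, HR 0.5, sustained). The upper end needs an effect that lasts well beyond the last ipilimumab dose.

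It would go too far to say that TTP and PFS are uninterpretable, since they remain valid descriptions of the perioperative strategy. It would also go too far to say that presurgical efficacy has no possible measure, since the week-6 scan is already scheduled.

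**What to change.** 1. In 2.0 and 12.1, state TTP and PFS as estimates for the perioperative strategy as assigned: presurgical drug, resection and adjuvant drug. Describe the adjuvant phase in 12.1 so that it matches 5.3.
2. In 12.6, state that TTP and PFS, by arm or as a difference between arms, will not be interpreted as effects of presurgical treatment alone.
3. Assess presurgical efficacy by RECIST 1.1 response and progression at the week-6 pre-surgery scan, by arm, over all randomized patients. Reconcile this with the ORR timing in 12.2.2.1 (after 12 weeks of therapy) and the week-14 response assessment in 12.6, both of which fall after planned resection.
4. Optionally, report by arm the proportion not resected because of progression, which 5.3 anticipates in 1 to 3 of 30 patients. This depends on the reason being recorded, which the documents do not show.

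The cost is a few sentences and one short descriptive table, with no extra patients, scans or procedures, so it remains feasible although enrollment has stopped. The downside is a narrower claim for TTP and PFS. No treatment change is proposed.

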3.0 DISEASE BACKGROUND

3.1 Hepatocellular Carcinoma

Hepatocellular carcinoma (HCC) is a highly lethal malignancy of worldwide significance and has become increasingly important in the United States. Overall, it is the most common

primary liver cancer, the sixth most common cancer, and the third most common cause of cancer-related deaths worldwide [1]. Various risk factors are responsible for the majority of HCC cases. these include liver cirrhosis (multiple etiologies), hepatitis B virus (HBV) infection, hepatitis C virus (HCV) infection, alcohol abuse, and non-alcoholic fatty liver disease [2]. Notably, although treatment for HCV has dramatically improved over the past several years, HCC incidence in the United States is rising especially among patients chronically infected with HCV. This is likely due to the long latency period between initial HCV infection and HCC incidence [3, 4].

Treatment options for HCC depend on the cancer stage at initial presentation and degree of synthetic liver dysfunction. Although a number of different staging systems have been used to provide accurate prognostic assessment (i.e. AJCC, Okuda, GRETCH, CLIP, etc.), all have limitations. The Barcelona Clinic Liver Cancer staging system provides an easy reference algorithm that links HCC stage and evidence-based treatment recommendations (Fig. 1) [5-7].

Nature Reviews | Disease Primers

Figure 1: BCLC staging system and therapeutic strategy. Llovet, J. M. *et al.* (2016) Hepatocellular carcinoma *Nat. Rev. Dis. Primers* doi:10.1038/nrdp.2016.18

3.2 Standard Therapy for Hepatocellular Carcinoma

Surgical Resection and Liver Transplantation

The only potentially curative treatment modalities for HCC include surgical resection (partial hepatectomy) and liver transplantation. Unfortunately, the actual number of patients who qualify for these modalities is small (approximately 10-30%) because most patients present with locally advanced or metastatic disease, or have significant liver dysfunction that precludes curative options. Surgical resection is typically considered for patients with a solitary tumor of any size who have adequate liver remnant and no evidence of major vascular invasion or portal hypertension [8]. Recent evidence has shown that partial hepatectomy procedures in carefully selected patients can be done with low operative morbidity and mortality [9, 10]. However, despite these favorable surgical outcomes, in those patients who are fortunate to undergo surgical resection, tumor recurrence is common. In fact, the 5-year tumor recurrence rate following surgical resection have been reported to be as high as 70% [11-13].

Although there is no FDA-approved medication for use in the adjuvant setting after surgical resection, the recently reported phase III STORM trial evaluated the efficacy and safety of sorafenib, an antiangiogenic agent approved for use in advanced HCC [14]. In this study, 1,114 HCC patients with a complete radiological response after surgical resection or local ablative therapy were given sorafenib 400 mg or placebo twice a day for a maximum of 4 years. Treatment related adverse events were high in both study groups and there was no difference seen between the two groups in regard to recurrence-free survival (RFS), time to recurrence (TTR) or overall survival (OS). At this time, there remains no evidence to support a particular adjuvant therapy in HCC. Of note, our pilot study is important as it will generate for the first time PFS data in HCC with combination nivolumab plus ipilimumab.

Liver transplantation is the other potentially curative treatment option for HCC patients that removes both the underlying HCC tumors and background cirrhosis. In 1996, Mazzaferro and colleagues proposed the Milan criteria (single lesion \leq 5 cm or 2-3 lesions each \leq 3 cm, no macrovascular invasion, no extrahepatic disease) for patients with small, unresectable HCC in the setting of cirrhosis [15]. For patients meeting this criterion who underwent orthotopic liver transplantation, the OS and RFS rates at 4 years were 85% and 92%, respectively. Subsequent studies have confirmed the results reported in this initial Mazzaferro study. Because of this, the United Network for Organ Sharing (UNOS) has adopted the Milan criteria for determining candidates for liver transplantation with HCC. Moreover, in 2001, Yao and colleagues proposed expanded criteria (UCSF Criteria) for HCC liver transplantation (single lesion \leq 6.5 cm or 2-3 lesions, each \leq 4.5 cm + sum of lesions \leq 8 cm, no macrovascular invasion, no extrahepatic disease) that demonstrated 1- and 5-year survival rates of 90% and 75%, respectively [16]. Because

UNOS specifies that patients undergoing evaluation for liver transplantation are not eligible for partial hepatectomy, liver transplantation is usually reserved for those patients with early-stage HCC and moderate to severe cirrhosis (i.e., Child's Pugh B or C). On the other hand, partial hepatectomy is considered for those patients with mild cirrhosis (i.e., Child's Pugh A) having an HCC tumor amenable to resection as deemed by the performing surgeon.

Local-regional therapies for HCC

Conceptually, local-regional therapies are designed to induce local tumor necrosis and are indicated for those patients with primarily liver-only disease but who are not resection or transplantation candidates. Even though there is no absolute HCC size-cut off for use of these treatment modalities, there are a number of contraindications to use. These include poor synthetic liver function (i.e. Child Pugh C), elevated bilirubin > 2.5, significant ascites, hepatic encephalopathy, recent variceal bleeding, and main portal vein thrombosis. Local-regional therapies are generally divided into two categories: ablation and arterially directed therapies.

Ablative modalities include thermal ablation (radiofrequency ablation or microwave ablation), cryoablation, or chemical ablation (percutaneous ethanol infusion or acetic acid injection). Ablative procedures may be curative in treating tumors ≤ 3 cm and have shown increased overall survival in tumors 3 - 5 cm in largest diameter [17-19]. Radiofrequency ablation (RFA), which we consider the most commonly used method of the ablative options, involves the local application of radiofrequency thermal energy to small HCC lesions. In fact, some centers even consider RFA the treatment of choice for small tumors (<2 cm) in an appropriate location. This is based on studies demonstrating similar outcomes for these tumors when compared to surgical resection with less cost and procedure-related complications [20].

Arterial directed therapies involve selective catheter-based infusion of particular substances into the hepatic artery. These therapies are possible because the liver has a dual blood supply; the portal vein supplies blood to normal liver parenchyma whereas the hepatic artery supplies blood to HCC lesions. Such modalities are particularly attractive because all tumors, irrespective of location, can be treated with an arterial approach provided the blood supply to the tumor can be manipulated without causing undo harm to surrounding, normal tissue. In general, arterial based treatments are used for larger tumors not amenable to resection, transplantation or an ablative approach. Currently available arterial directed therapies include transarterial bland embolization, transarterial chemoembolization, transarterial radioembolization and yttrium-90 microspheres.

External-beam Radiation Therapy (EBRT)

Because HCC is a radiosensitive tumor, EBRT can be employed in patients with unresectable or inoperable HCC to deliver high doses of radiation to the underlying HCC tumors while sparing the normal liver parenchyma. Like arterial based approaches, EBRT can be used to treat all tumor regardless of location. Specific EBRT modalities include intensity-modulated radiation therapy (IMRT), stereotactic body radiation therapy (SBRT), and proton beam therapy (PBT). Notably, SBRT is usually considered in patients with liver-only disease who have failed ablative or arterial-based approaches, and for those with partial vein thrombosis [21].

Sorafenib for advanced HCC

Sorafenib is an orally bioavailable agent originally developed as a Raf kinase inhibitor. Further studies revealed that sorafenib was also a potent inhibitor of vascular endothelial growth factor receptors (VEGFR-1, -2, and -3), as well as platelet derived growth factor receptor (PDGFR), KIT and FLT3. Currently, sorafenib is the only FDA-approved therapy for advanced or unresectable HCC. This approval was based on the phase III SHARP study, which evaluated 602 patients with advanced HCC who had not received previous systemic therapy who received either sorafenib (400 mg BID) or placebo [22]. Median overall survival was 10.7 months in the sorafenib group compared to 7.9 months in the placebo group; there was also a benefit in time to symptomatic progression (5.5 months for sorafenib vs. 2.8 months for placebo). Additionally, in the phase III Asia-Pacific study, 226 patients with advanced HCC were randomized to receive either sorafenib (400 mg BID) or placebo [23]. This study, which included a large number of HBV infected patients, also demonstrated improved OS (6.5 months vs. 4.2 months) and TTP (2.8 months for 1.4 months) for the sorafenib group.

Of note, there currently is no second line therapy approved for advanced HCC.

Regorafenib for advanced HCC

Regorafenib is an orally bioavailable agent that inhibits multiple membrane-bound and intracellular kinases involved in cell growth (RET, VEGFR-1, VEGFR-2, VEGFR-3, KIT, PDGFR-alpha, PDGFR-beta, FGFR1, FGFR2, TIE2, DDR2, Trk2A, Eph2A, RAF-1, BRAF, SAPK2, PTK5 and ABI). Although regorafenib is not yet approved for advanced HCC, the recently reported phase III RESORCE Trial evaluated 573 patients with intermediate or advanced stage HCC who had been previously treated with sorafenib (data unpublished). Patients were randomized 2:1 to receive either regorafenib 160 mg daily or placebo for 1-3 of each four-week cycle. This trial, which has not been formally published, demonstrated improvements in both

median OS (10.6 months vs. 7.8 months) and PFS (3.1 months vs. 1.5 months) for the regorafenib group.

Other systemic therapies for advanced HCC

Multiple chemotherapy regimens and targeted agents have been tested in advanced HCC with modest benefit; however, no single regimen has shown superiority to any other. Most randomized trials have demonstrated median OS benefits of < 12 months. Monotherapy agents that have been tested in HCC include doxorubicin, epirubicin, mitoxantrone, 5-fluorouracil (5-FU), capecitabine, gemcitabine, irinotecan, thalidomide, cisplatin, bevacizumab (VEGF inhibitor) and ramcirumab (VEGF inhibitor). In addition, a number of combination chemotherapy regimens have also been tested with limited clinical efficacy. These include FOLFOX (infusional 5-fluorouracil, leucovorin, oxaliplatin), cisplatin doublets, gemcitabine doublets and PIAF (cisplatin, interferon alpha, doxorubicin, and infusional 5-FU). Notably, our group recently performed a clinical trial which tested the efficacy of modified PIAF in patients without cirrhosis or hepatitis who had initially unresectable HCC [24]. Our results demonstrated an ORR=36% and a rate of conversion to curative surgery = 33%.

